### **11.2.3 Expedited reporting of AEs to DAIDS**

Requirements, definitions, and methods for expedited reporting of AEs to DAIDS are outlined in Version 2.0 (January 2010) of the *Manual for Expedited Reporting of Adverse Events to DAIDS* (DAIDS EAE Manual), which is available on the RSC website at <http://rsc.tech-res.com/safetyandpharmacovigilance/>. The SAE Reporting Category will be used.

The internet-based DAIDS Adverse Experience Reporting System (DAERS) must be used for expedited AE (EAE) reporting to DAIDS. In the event of system outages or technical difficulties, expedited AE reports may be submitted via the DAIDS EAE Form. This form is available on the DAIDS RSC website at <http://rsc.tech-res.com/clinical-research-sites/safety-reporting/daims/paper-eae-reporting>.

For questions about DAERS, please contact [contact] or from within the DAERS application itself. For questions about expedited reporting, please contact the DAIDS RSC Safety Office at [contact].

Under ICH E2A (*Clinical Safety Data Management: Definitions and Standards for Expedited Reporting*), an SAE is defined as any untoward medical occurrence that at any dose:

- results in death,
- is life-threatening (Note: The term “life-threatening” in the definition of “serious” refers to an event in which the patient was at risk of death at the time of the event; it does not refer to an event, which hypothetically might have caused death, if it were more severe),
- requires patient hospitalisation or prolongation of existing hospitalisation,
- results in persistent or significant disability/incapacity,
- is a congenital anomaly/birth defect, or
- is a medically important event or reaction

Medical and scientific judgment should be exercised when deciding if other situations are serious. Such instances could include medical events that may not be immediately life-threatening or result in death or hospitalization, but which may jeopardize the patient or may require intervention to prevent one of the outcomes listed in the definition above. Examples of such events are intensive treatment in an emergency room or at home for allergic bronchospasm, blood dyscrasias or convulsions not resulting in hospitalization, or development of drug dependency or drug abuse.

The expedited reporting period for this study comprises the entire study period for each individual participant (from study enrolment until study completion or discontinuation from the study).

The study products that must be considered in determining relationships of AEs requiring expedited reporting to DAIDS and pertinent national regulatory authorities are:

- ALVAC-HIV (vCP2438)
- Bivalent Subtype C gp120/MF59®
- Bivalent Subtype C gp120 admixed with Aluminum Hydroxide
- Bivalent Subtype C gp120

Clinic staff will report SAEs as indicated in Section 11.3, *Safety pause and prompt PSRT AE review* to HVTN Core or within 3 working days for SAEs not described in Table 11-1, *AE notification and safety pause/AE review rules*, in addition to completing the standard AE form.

#### 11.2.4 Expedited reporting of AEs to regulatory authorities

The study sponsor or designee(s) prepares and files expedited reports to appropriate regulatory authorities within the timelines required by pertinent national regulatory authorities. SAEs will be reported to the South Africa Medicines Control Council (MCC) within 24 hours of the sponsor becoming aware of each event followed, as needed, with full safety reports deemed reasonably related to study product within the time frame specified in the MCC guidelines.

Site IoRs/designees will submit EAE information and any other relevant safety information to their ECs/IRBs in accordance with EC/IRB requirements.

### 11.3 Safety pause and prompt PSRT AE review

When a trial is placed on safety pause, all enrollment and vaccination with the product related to the event that triggered the pause will be held until further notice. The AEs that will lead to a safety pause or prompt HVTN 107 PSRT AE review are summarized in Table 11-1. Vaccinations may be suspended for safety concerns other than those described in the table, or before pause rules are met, if, in the judgment of the HVTN 107 PSRT, participant safety may be threatened. Criteria for an individual participant's departure from the schedule of vaccinations are listed in Section 7.3.

**Table 11-1 AE notification and safety pause/AE review rules**

Event and relationship to study products	Severity	HVTN CRS action	HVTN Core action
SAE, related	Grade 5 or Grade 4	Phone immediately, email and submit forms immediately a	Immediate pause
SAE, not related	Grade 5	Phone immediately, email and submit forms immediately a	Immediate HVTN 107 PSRT notification
SAE, related	Grade 3	Email and submit forms immediately	Prompt HVTN 107 PSRT AE review to consider pause
AE b , related	Grade 4 or Grade 3	Email and submit forms immediately	Prompt HVTN 107 PSRT AE review to consider pause

a Phone numbers and email addresses are found in the Key Contacts under Safety Reporting and Clinical Monitoring on the HVTN 107 home page.

b Does not include subjective reactogenicity symptoms (injection site pain, tenderness, fatigue/malaise, myalgia, arthralgia, chills, headache, nausea).

For all safety pauses, HVTN Core notifies the HVTN 107 PSRT, HVTN Regulatory Affairs, DAIDS Pharmaceutical Affairs Branch (PAB), DAIDS Regulatory Affairs Branch (RAB), DAIDS Safety and Pharmacovigilance Team (SPT), and participating HVTN CRSs. When an immediate safety pause is triggered, HVTN Core notifies the SMB.

Once a trial is paused, the HVTN 107 PSRT reviews safety data and decides whether the pause can be lifted or permanent discontinuation of vaccination is appropriate, consulting

the SMB if necessary. HVTN Core notifies the participating HVTN CRSs, HVTN Regulatory Affairs, DAIDS PAB, DAIDS RAB, and DAIDS SPT of the decision regarding resumption or discontinuation of study vaccinations. Based on the HVTN 107 PSRT assessment, the trial sponsor or designee(s) notifies pertinent national regulatory authorities as needed.

If an immediate HVTN 107 PSRT notification or prompt HVTN 107 PSRT AE review is triggered, HVTN Core notifies the HVTN 107 PSRT as soon as possible during working hours (US Pacific Time)—or, if the information was received during off hours, by the morning of the next work day. If a prompt HVTN 107 PSRT AE review cannot be completed within 72 hours of notification (excluding weekends and US federal holidays), an automatic safety pause occurs.

The HVTN requires that each CRS submit to its IRB/EC protocol-related safety information (such as safety reports, notification of vaccine holds due to the pause rules, and notification of other unplanned safety pauses). CRSs must also follow all applicable RE reporting requirements.

In addition, all other AEs are reviewed routinely by the HVTN 107 PSRT (see Section 11.4.2).

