### **7.3.3 Discontinuing vaccination for a participant**

Under certain circumstances, an individual participant's vaccinations will be permanently discontinued. Specific events that will result in stopping a participant's vaccination schedule include:

- Co-enrollment in a study with an investigational research agent (rare exceptions allowing for the continuation of vaccinations may be granted with the unanimous consent of the HVTN 107 PSRT).
- Clinically significant condition (ie, a condition that affects the immune system or for which continued vaccinations and/or blood draws may pose additional risk), including but not limited to the following:
  - Pregnancy (Vaccinations will be stopped while a participant is pregnant. If the participant is no longer pregnant and can be vaccinated within an appropriate visit window, vaccinations may resume, see Section 7.3.1);
  - Any grade 4 local or systemic reactogenicity symptom, lab abnormality, or AE that is subsequently considered to be related to vaccination;

- Any grade 3 lab abnormality or other clinical AE (exception: fever or vomiting and subjective local and systemic symptoms) that is subsequently considered to be related to vaccination; upon review, the PSRT may allow continuation of vaccination if the participant has grade 3 erythema and/or induration;
- SAE that is subsequently considered to be related to vaccination;
- Clinically significant type 1 hypersensitivity reaction associated with study vaccination. Consultation with the HVTN 107 PSRT is required prior to subsequent vaccinations following any type 1 hypersensitivity reaction associated with study vaccination; or
- Investigator determination in consultation with Protocol Team leadership (eg, for repeated nonadherence to study staff instructions).
- A study participant who misses a study injection is permitted to continue with subsequent study injections that can still be scheduled within the time interval specified in the *HVTN 107 Study Specified Procedures* (SSP) unless there is a protocol-mandated reason for discontinuation.

Such participants should be counseled on the importance of continuing with the study and strongly encouraged to participate in follow-up visits and protocol-related procedures per the protocol for the remainder of the trial, unless medically contraindicated.

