### **11.4.2 Weekly review**

During the injection phase of the trial, the HVTN 107 PSRT reviews clinical safety reports on a weekly basis and conducts calls to review the data as appropriate. After the injections and the final 2-week safety visits are completed, less frequent reporting and safety reviews may be conducted at the discretion of the HVTN 107 PSRT. HVTN Core reviews reports of clinical and laboratory AEs. Events identified during the review that are considered questionable, inconsistent, or unexplained are referred to the HVTN CRS clinic coordinator for verification.

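### Table 11-1 footnote b takes eight subjective reactogenicity symptoms out of prompt PSRT review at Grade 4 as well as Grade 3; limiting it to Grade 3 is a cheap improvement

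*Combined protocol and SAP*

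**What the plan says.** **Trial-level rule (Section 11.3, Table 11-1).** One row covers related AEs that are not SAEs, at Grade 4 or Grade 3. The site must email and submit forms immediately, and the PSRT must promptly review the event to consider a pause. Footnote b qualifies that row: "Does not include subjective reactogenicity symptoms (injection site pain, tenderness, fatigue/malaise, myalgia, arthralgia, chills, headache, nausea"). If a prompt review cannot be completed "within 72 hours of notification (excluding weekends and US federal holidays), an automatic safety pause occurs". Core notifies the PSRT during working hours or, "if the information was received during off hours, by the morning of the next work day". For events outside the table, "all other AEs are reviewed routinely by the HVTN 107 PSRT (see Section 11.4.2"), and Section 11.4.2 says: "During the injection phase of the trial, the HVTN 107 PSRT reviews clinical safety reports on a weekly basis".

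Footnote b is not attached to the SAE rows. A related Grade 4 or 5 SAE causes an immediate pause whatever the symptom.

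**Participant-level rule (Section 7.3.3).** Three of the events that permanently end a participant's vaccinations matter here.
- The Grade 4 item is "Any grade 4 local or systemic reactogenicity symptom, lab abnormality, or AE that is subsequently considered to be related to vaccination". It makes no exception by type of symptom.
- The Grade 3 item, again for related events, does carve some out: "Any grade 3 lab abnormality or other clinical AE (exception: fever or vomiting and subjective local and systemic symptoms").
- The item for serious events is "SAE that is subsequently considered to be related to vaccination".

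The exception for subjective symptoms stands only in the Grade 3 item.

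**The concern.** At Grade 3 the two rules agree for the eight symptoms: the participant goes on being vaccinated and no prompt review is required. At Grade 4 they part. A related, non-serious Grade 4 headache, myalgia or injection site pain is grave enough to bar that person from further doses, but nothing fixes a time by which the PSRT must consider whether others should keep receiving the same product. The documents give no reason for carrying the exemption up to Grade 4.

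The resulting order is odd. Related Grade 3 erythema (10 cm or more across, Section 11.2.2) and related Grade 4 vomiting are not in footnote b, so both get prompt review, while a related Grade 4 headache that is not an SAE does not.

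The exemption also carries into other checks. Core's listed monitoring duties (11.1.4), its daily review (11.4.1) and the site's assessment of each AE (11.2.2) all refer to the pause and prompt-review criteria of Section 11.3. What is at stake is the timing of a PSRT decision on continued dosing. No endpoint, power figure or sample size is involved.

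**Working it through.** **1. The rules side by side (related events)**

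| Event | Participant stopped (7.3.3)? | Trial-level action (11.3) |
|---|---|---|
| Grade 3 subjective symptom, not an SAE | No | Routine review |
| Grade 4 subjective symptom, not an SAE | Yes | Routine review |
| Grade 3 erythema | Yes, unless the PSRT allows continuation | Prompt review |
| Grade 3 fever or vomiting, not an SAE | No | Prompt review |
| Grade 4 subjective symptom that is an SAE | Yes | Immediate pause |

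Row 2 is the point. Row 4 shows that the two sections differ in the other direction as well.

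**2. How long prompt review may take.** The limit is 72 hours from PSRT notification, excluding weekends (Section 11.3).
- Notified Monday or Tuesday: 3 calendar days.
- Notified Wednesday, Thursday or Friday: 72 hours plus a weekend = 5 days.
- Reported off hours and notified the next work morning: up to about 5.7 days (Friday evening to Thursday morning).

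Against a worst-case 7-day wait for weekly review, the time saved is 7 − 3 = 4 days, 7 − 5 = 2 days, or about 1 day. A Monday US federal holiday can remove the saving.

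**3. Vaccination visits in that time.** Inputs: 132 participants, 96 of them in Groups 1, 2 and 4 with a Month 3 dose (Table 3-1), and a 3-month accrual period (Section 6.1). Assumption: even accrual over 13 weeks.
- First doses: 132/13 = 10.2 per week. Month 3 doses: 96/13 = 7.4 per week.
- Peak is week 12 to 13, when Month 0, 1 and 3 doses overlap: 10.15 + 10.15 + 7.38 = 27.7 visits per week.
- Visits in d days = weekly rate × d/7.

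| Days saved | Peak week (27.7) | At 10.2 per week |
|---|---|---|
| 4 | 15.8 | 5.8 |
| 2 | 7.9 | 2.9 |
| 1 | 4.0 | 1.5 |
| 6 (review done in 1 day) | 23.7 | 8.7 |

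**4. Average rather than worst case.** Assume the report hour is uniform over the week, working hours are 09:00 to 17:00, the wait for weekly review is uniform on 0 to 7 days, and prompt review always runs to its limit L, measured from the report.
- Mean L = 4.5 days.
- For a given L, the mean saving is (7 − L)²/14. Averaged over report times this is about 0.5 day.
- Weekly review falls later than the limit with probability (7 − L)/7, on average 36%.
- Visits: 27.7 × 0.5/7 = 2.0 in the peak week; 10.2 × 0.5/7 = 0.7 at the lower rate.

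**5. How many extra reviews.** With no events in n, the score upper 95% bound is 3.84/(n + 3.84).
- HVTN 097, no Grade 4 AEs (Section 4.11.3.3), 80 vaccine recipients (Table 4-10): 3.84/83.84 = 4.6%; × 132 = 6.0. This assumes the reported count includes reactogenicity.
- If none of the 210 HVTN 100 vaccine recipients had a Grade 4 reaction: 3.84/213.84 = 1.8%; × 132 = 2.4. That zero is an assumption. The visible interim text is blinded, partly removed, and describes severe reactions only.

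**The case against.** The strongest reply is that the rules were never meant to match. Section 7.3 concerns the individual and sends trial pauses to Section 11.3, which sends individual criteria back. They also differ on Grade 3 fever and vomiting, which the proposed change leaves alone. This stands, so a reader who infers that the protocol contradicts itself goes too far.

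Second, the affected class may be nearly empty. It holds only related Grade 4 subjective symptoms that are not SAEs. Section 4.11.3.3 glosses Grade 4 as life threatening, and the SAE definition in Section 11.2.3 includes medically important events. The overlap is not shown to be complete: that definition of life-threatening requires actual risk of death at the time, and Table 11-1 itself has a Grade 4 row for AEs that are not SAEs. The DAIDS grading table, which would settle how Grade 4 pain or headache is graded, is not in the documents.

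Third, a reader might infer that such an event could go unnoticed. The documents do not support that. Section 2.5 says Core monitors safety daily. Forms are due by the end of the next business day (11.2.1), participants are to report daily during the reactogenicity period, and a reaction above mild is in general seen by a clinician within 48 hours (9.10). Sites must report AEs leading to discontinuation and are expected to notify clinical safety staff of serious concerns, by phone where immediate attention is needed (11.2.2). The PSRT may suspend vaccination at its discretion (11.3). What remains is narrow: none of these sets a deadline for PSRT consideration.

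**Conclusion.** The point holds as a small gap in timing. Confidence is high for the wording difference and low that it will ever affect a participant. Severity is minor.

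The fair measure of size is the average gain of about 0.5 day, which rests on the timing assumptions in step 4 of the working. On those assumptions weekly review comes no later than the prompt-review limit about 64% of the time (100% − 36%). Faster prompt review would gain more. The figure of about 16 visits should not be read as doses prevented: it needs a full 7-day wait, a Monday or Tuesday notification and the single peak week, and prompt review does not itself stop dosing. All visit counts depend on even accrual.

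**What to change.** In footnote b to Table 11-1, insert the words Grade 3 before subjective, so that the exemption covers Grade 3 symptoms only. Every related Grade 4 AE would then bring an immediate site email, fall within Core's listed daily-review triggers and go to prompt PSRT review. Leave Section 7.3.3 and the Grade 3 exemption as they are.

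The change is two words and can go into the next protocol modification by whichever route in Section 13 the sponsor requires. The downside is a few extra PSRT reviews: at most about 6 on the HVTN 097 bound, or about 2 on the HVTN 100 assumption. Each would carry an automatic pause if not completed in time. Visits and sample size do not change.

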## **11.4 Review of cumulative safety data**

Routine safety review occurs at the start of enrollment and then throughout the study.

Reviews proceed from a standardized set of protocol-specific safety data reports. These reports are produced by the SDMC and include queries to the HVTN CRSs. Events are tracked by internal reports until resolution.

### **11.4.1 Daily review**

Blinded daily safety reviews are routinely conducted by HVTN Core for events requiring expedited reporting to DAIDS, and events that meet safety pause criteria or prompt HVTN 107 PSRT AE review criteria.

### **11.4.2 Weekly review**

During the injection phase of the trial, the HVTN 107 PSRT reviews clinical safety reports on a weekly basis and conducts calls to review the data as appropriate. After the injections and the final 2-week safety visits are completed, less frequent reporting and safety reviews may be conducted at the discretion of the HVTN 107 PSRT. HVTN Core reviews reports of clinical and laboratory AEs. Events identified during the review that are considered questionable, inconsistent, or unexplained are referred to the HVTN CRS clinic coordinator for verification.

## **11.5 Study termination**

This study may be terminated early by the determination of the HVTN 107 PSRT, the MCC or other pertinent national regulatory authority, NIH, Office for Human Research Protections (OHRP), or vaccine developer(s). In addition, the conduct of this study at an

individual HVTN CRS may be terminated by the determination of the IRB/EC and any applicable RE.

## 12 Protocol conduct

This protocol and all actions and activities connected with it will be conducted in compliance with the principles of GCP (ICHe6), and according to DAIDS and HVTN policies and procedures as specified in the *HVTN Manual of Operations*, DAIDS Clinical Research Policies and Standard Procedures Documents including procedures for the following:

- Protocol registration, activation, and implementation;
- Informed consent, screening, and enrollment;
- Study participant reimbursement;
- Clinical and safety assessments;
- Safety monitoring and reporting;
- Data collection, documentation, transfer, and storage;
- Participant confidentiality;
- Study follow-up and close-out;
- Unblinding of staff and participants;
- Quality control;
- Protocol monitoring and compliance;
- Advocacy and assistance to participants regarding negative social impacts associated with the vaccine trial;
- Risk reduction counseling;
- Specimen collection, processing, and analysis;
- Ancillary studies, and
- Destruction of specimens.

Any policies or procedures that vary from DAIDS and HVTN standards or require additional instructions (eg, instructions for randomization specific to this study) will be described in the HVTN 107 *Study Specific Procedures*.

### 12.1 Social impacts

Participants in this study risk experiencing discrimination or other personal problems, resulting from the study participation itself or from the development of VISP. The HVTN CRS is obliged to provide advocacy for and assistance to participants regarding these negative social impacts associated with the vaccine trial. If HVTN CRS staff have questions regarding ways to assist a participant dealing with a social impact, a designated NIAID or HVTN Core representative can be contacted.

Social harms are tabulated by the SDMC and are subjected to descriptive analysis. The goal is to reduce their incidence and enhance the ability of study staff to mitigate them when possible.

Summary tables of social impact events will be generated weekly, and made available for review by the protocol chairs, protocol team leader, and the designated NIAID representative.

## **12.2 Compliance with NIH guidelines for research involving products containing recombinant DNA**

Because this study is evaluating products containing recombinant DNA, it must comply with regulations set forth in the NIH's *Guidelines for Research Involving Recombinant or Synthetic Nucleic Acid Molecules*. Information about the study must be submitted to site Institutional Biosafety Committees (IBC) and must be approved before participants are enrolled at the site. Investigators at each site are responsible for obtaining IBC approval per NIH guidelines *section IV-B07-a-(1)*. IBC review and approval must be documented by the investigator and submitted as part of initial protocol registration for this trial. If this protocol is amended, investigators should follow the requirements of their IBC.

## **12.3 Specific regulatory considerations for Republic of South Africa and other Southern African countries**

The Republic of South Africa has laws regarding the use, manufacture, importation, and experimentation of products which are genetically modified. These are contained in the Genetically Modified Organism (GMO) Act 15 of 1997, administered by the South African National Department of Agriculture, Pretoria. The Registrar of GMO shall be consulted on all formal developments relating to this protocol and clinical trial, and as required, a formal application will be made to the Registrar of GMO to review the HVTN 107 clinical trial, to obtain approval for the proposed clinical trial and for the importation of the study products.

Any regulations specific to other countries containing CRSs at which HVTN 107 will be implemented will also be observed.

